7.1 Subject Disposition

Subject disposition data will be provided for:

- The number of subjects enrolled at each site [REDACTED]
- Compliance to the follow-up visit schedule
- The number and percentage of subjects by discontinuation reason

7.2 Baseline Summary

Baseline characteristics such as subject demographics, clinical history, risk factors, and history of peripheral intervention will be summarized using descriptive statistics.

[figure not shown]
7.4 Primary Outcome Measure Analysis

Analysis of the primary outcome measure of Procedural Success will be assessed post-procedure on the ITT analysis set. Procedural Success is comprised of:

- Successful completion of OA treatment via transradial access determined by use of the device within the target lesion
- The presence of no serious transradial access related events. TRA related events include:
 - Serious TRA site bleeding (BARC Type 2-5)
 - Serious TRA site hematoma
 - Serious radial artery spasm
 - Serious hand ischemia
 - Stroke
 - Transient Ischemic Attack (TIA)
 - Serious nerve damage
 - Perforation
 - TRA site pseudoaneurysm

Procedural Success is considered successful for a subject if all criteria are met.

A large rectangular area of the page is completely blacked out, indicating redacted content. It is positioned below the 'Procedural Success' text and above the page footer.

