## 7.1 Primary Outcome: Procedural Success

Procedural success is defined as successful completion of OA treatment of the target lesion via transradial access without serious transradial access related events.

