### 9.2 Index Procedure Inclusion Criteria

1. Physician obtains successful radial artery access (Note: snuffbox access is allowed)
2. Target lesion appropriate (i.e. location/morphology) for OA treatment via TRA within target area
3. OAS use attempted (defined as ViperWire introduced into the body)

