**Prior to insertion of ViperWire:**

4. Femoral access is obtained
5. Unsuccessful peripheral intervention
6. A reportable adverse event has occurred

[figure not shown]

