### **9.6 Point of Enrollment**

Enrollment is defined as point when a subject has signed an IRB-approved ICF, have met all inclusion criteria and none of the exclusion criteria, and the ViperWire has been inserted into the body.

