2.1 Primary Outcome Measure: Procedural Success

Procedural success is defined as successful completion of OA treatment of the target lesion via transradial access (TRA) without serious transradial access related events.

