5.1 Intent to Treat (ITT) Analysis Set

The ITT analysis set will include all enrolled subjects who have been enrolled regardless of deviations from the protocol.

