7. REQUIRED DATA ANALYSES

The following analyses will be performed on the ITT population unless otherwise noted. Analyses will occur on the target lesion, defined as the stenotic segment appropriate for treatment with the Orbital Atherectomy System study device(s) via transradial access. The target lesion will be:

- The first lesion with Orbital Atherectomy attempted OR
- The first lesion with Orbital Atherectomy attempted after other successful peripheral intervention(s) without the occurrence of a reportable adverse event.

The study will be limited to one (1) target lesion per enrolled subject.

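### SAP 7.4, in its readable text, scores completion of orbital atherectomy by device use in the target lesion, so a treatment started via radial access and then abandoned can count as Procedural Success

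*SAP*

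**What the plan says.** Protocol 7.1 defines the primary outcome, Procedural Success, as "successful completion of OA treatment of the target lesion via transradial access", with no serious TRA related event. SAP 2.1 repeats this: "successful completion of OA treatment of the target lesion via transradial access (TRA) without serious transradial access related events". Neither section says how completion is to be judged.

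SAP 7.4 turns the definition into two criteria, both of which must be met. The second is the absence of serious TRA related events, from a list. The first is "Successful completion of OA treatment via transradial access determined by use of the device within the target lesion".

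Three other provisions decide which subjects reach this rule:

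- **Attempt.** Protocol 9.2 gives an attempt its own definition: "OAS use attempted (defined as ViperWire introduced into the body". SAP 7 picks the target lesion by attempt: "The first lesion with Orbital Atherectomy attempted".
- **Enrollment.** Under Protocol 9.6 a subject who has consented and is eligible is enrolled once "the ViperWire has been inserted into the body".
- **Analysis set.** SAP 5.1 keeps "all enrolled subjects who have been enrolled regardless of deviations from the protocol", and SAP 7.4 applies the primary outcome to that set.

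**The concern.** Starting OA in a lesion and completing it are different events, and the outcome is named and defined by the second. The SAP 7.4 bullet keeps the word completion but makes device use the test of it. Device use is satisfied as soon as the device has worked in the lesion, whatever follows.

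The study exists to describe acute results of OA from the radial artery, and this is its primary outcome. The study is single-arm, described as hypothesis generating, and not powered, so no readable test or threshold hangs on the rate. What is at stake is the reported rate and its confidence interval. Scoring device use as completion can leave them unchanged or move them upward, never downward.

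**Working it through.** The documents give no target rate, power or derived sample size for this outcome, so there is no figure of the plan's own to reproduce. The check compares the texts and then sizes the effect.

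**Step 1. Apply the readable rule to each kind of enrolled subject.** All are in the intent-to-treat set, because enrollment occurs at wire insertion, before completion can be known.

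| Course after enrollment | SAP 7.4, criterion 1 | SAP 7.4, criterion 2 | Score under 7.4 | Completed via TRA (Protocol 7.1)? |
|---|---|---|---|---|
| Wire inserted, device never used in the lesion | not met | any | failure | no |
| OA started in the lesion via TRA, stopped because of a listed serious TRA event | met on device use | not met | failure | no |
| OA started in the lesion via TRA, abandoned for another reason, no listed event | met on device use | met | **success** | **no** |
| OA completed via TRA, no listed event | met | met | success | yes |

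Only the third row is scored differently from the definition. An example is a stop for radial spasm that is not serious, since the event list counts only serious spasm.

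**Step 2. See whether the secondary outcome catches the third row.** Treatment Success (Protocol 7.2, SAP 2.2) depends on residual stenosis, stent placement and significant angiographic complications. It has no condition on completing OA or on access route. It flags an abandoned OA only if the residual stenosis is too high or such a complication occurred, and it does not alter the primary score in any case.

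**Step 3. Size per subject.** Inputs: N = 50 (Protocol 8.0 and SAP 3.1, approximate) and alpha 0.05 for confidence intervals (SAP 6.2). The readable text names no interval method, so the exact Clopper-Pearson method is assumed.

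- Shift per subject: 1/50 = 2.0 percentage points.
- Lower limit for x successes out of n: the 0.025 quantile of Beta(x, n − x + 1). Upper limit: the 0.975 quantile of Beta(x + 1, n − x), set to 1 when x = n.
- For x = n = 50 the lower limit reduces to 0.025^(1/50) = 0.929.

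If every other subject succeeds, SAP 7.4 reports 50/50 = 100% (92.9 to 100) in each row below:

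| OA abandoned but scored as success | Rate if scored as non-success | Exact 95% CI |
|---|---|---|
| 1 | 49/50 = 98% | 89.4 to 99.9 |
| 2 | 48/50 = 96% | 86.3 to 99.5 |
| 3 | 47/50 = 94% | 83.5 to 98.7 |

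**Step 4. How many such subjects?** The documents give no rate for OA abandoned after device use in the lesion. The 1.9% femoral crossover figure in the Protocol Introduction is a different quantity: it covers crossover generally, including for causes that could keep a device from reaching the lesion. It is not used here.

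**The case against.** **The SAP is entitled to operationalize an undefined term.** The readable protocol does not say what completion means, and device use in the lesion is an objective test. This has some force, but an operational rule should still measure the thing named. Device use measures delivery of the device. If delivery is what is wanted, the outcome should be labelled that way.

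**The literal reading is not the only one.** The bullet keeps the word completion, SAP 2.1 states the full definition, and SAP 1 says to read the plan with the protocol and CRFs. An analyst using all of these could fail an abandoned OA. That is possible, but the bullet says completion is determined by device use, which favours the looser scoring. If two analysts could score the same subject differently, the rule needs rewording anyway.

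**Much is unseen.** A block directly after the 7.4 criteria is blacked out, and the CRFs are not among the documents. This stands. A reader might infer that the plan never defines completion; the documents support only the statement that no definition is readable. Against this, the sentence requiring all criteria to be met comes before the blacked-out block, so the readable list looks complete, though a further rule cannot be excluded.

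**Conversion to femoral access.** A reader might also infer that OA started via TRA and finished only through another access site would be scored as a success. Protocol 9.4 does list "Femoral access is obtained" as an exclusion only before wire insertion, so such a subject stays enrolled. But the SAP 7.4 bullet keeps the requirement that completion be via TRA, so the text gives a ground for failing that subject. Conversion therefore does not support the finding; it merits only a clarifying sentence.

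**Conclusion.** The point holds for one group: subjects whose OA is started in the target lesion via TRA and then abandoned, with no listed serious TRA event. Under the readable SAP 7.4 they meet both criteria and can be scored as Procedural Success, although OA was not completed as Protocol 7.1 and SAP 2.1 require.

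The supportable size is 2.0 points per affected subject at N = 50, always upward. The count is unknown and may be zero, so a probability that the study contains such a subject would only restate an assumed rate; none is given.

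The conclusion rests on taking an abandoned treatment as not completed, on reading the bullet's device-use test as decisive, on about 50 subjects being enrolled, and on the redacted text and CRFs holding no completion rule. The interval figures also assume the exact method and no other failures. This should be fixed before the analysis, because it concerns the primary outcome, the direction of the bias is known and the change is small.

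**What to change.** 1. Reword the first bullet of SAP 7.4 so that success requires OA of the target lesion to be completed via TRA.
2. Record completion in a prespecified CRF item with two answers: OA completed, or OA discontinued before completion. Score the second as non-success.
3. State for clarity that OA finished only through non-radial access does not meet the TRA condition.
4. Report device use in the target lesion as a separate descriptive rate, so the delivery information is kept.
5. If redacted text or the CRF already sets these rules, replace steps 1 to 3 with a cross-reference in the bullet.

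The cost is one reworded bullet, one clarifying sentence and one CRF item if it is not already collected. There is a real downside: completion relies on operator report and is less objective than device use, which is a reason to fix the item's wording in advance. The reported rate may be slightly lower.

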7.8 Adverse Event (AE) Rates

Adverse event rates will be assessed on the ITT analysis set. All reportable adverse events specified in the protocol will be included in the analysis. Adverse events are collected starting at enrollment through subject exit from the study. AEs will be summarized by AE term and overall for number and percent of subjects experiencing each event, and number of events. AEs will also be summarized by AE category.

Adverse events summaries will be provided through study exit in the following groups:

- Serious Adverse Event (SAE): Any AE that meets the protocol definition of serious

Any events for which the determination of seriousness and/or relatedness to the device cannot be determined will count as serious and/or related for the purposes of this analysis.

No further analyses are planned outside those outlined in **Section 7 Required Data Analyses**. Any ad hoc analyses will follow the guidelines outlined in this document.

Page 11 of 11
